6.5.2. Weekly Visits through Radiation Therapy

During regular visits with medical staff, study subjects will also meet with study staff. Study staff will obtain photographs of the area of irradiation and collect the daily dairy forms. Study personnel will collect vital signs and the physician's assessment of the presence and quality of radiation dermatitis using the RTOG scale as well as the physician's assessment of skin dryness, appearance of inflammation, and the skin's natural barrier. Any adverse events will be noted and addressed. Subjects will complete the Dermatology Life Quality Index. Study personnel will provide KeraStat Cream, as needed, to subjects randomized to receive KeraStat Cream. Subjects randomized to standard of care will follow the instructions of their radiation oncologist. Study personnel will provide subjects with a daily diary form where subjects will note symptoms or treatment details of concern.

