11.2. Skin Appearance

The appearance of the skin (including dryness, appearance of inflammation, and the natural barrier) as observed and recorded by study staff as well as the patient's self-report of satisfaction with the appearance of skin during the RT and up to 10 weeks post-RT.

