12. STATISTICS

12.1. Description of Statistical Methods

Descriptive statistics will calculated and used to inform additional device development and to inform a power calculation for a follow on study, if required. The completion rate will be used as a measure of feasibility, with participants with an average of 10 or more applications per week being classified as compliant. A 95% confidence interval will be calculated around the estimate of compliance. After summary statistics are calculated by group, a t-test will be used to compare the two treatment groups for the effectiveness outcomes of DLQI score and RTOG score. A Fisher's exact test will be used to compare skin appearance issues between the groups. The counts for each type of adverse event will be summarized by grade and treatment group. For the KeraStat treatment group, the mean coverage will be calculated per square centimeter.

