12.2. Sample Size

Up to 26 subjects will be enrolled on this pilot study to assure completion of at least 24 subjects. The expected accrual rate is four per month with accrual lasting approximately six months. Participants will be randomized equally (n=12 per group) to standard of care or KeraStat Cream. With 12 participants in each treatment group expected to complete the study, we will be able to calculate a 95% confidence interval around the compliance rate in each group with a maximum margin of error of 0.283. Comparisons between groups for effectiveness (RTOG scale and DLQI score) will have 80 percent power to detect a difference of 1.2 standard deviations.

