12.3. Analysis of Patients Withdrawing Prematurely from the Study

All information for withdrawing subjects will be included in the analyses. Subjects who withdraw prematurely from the study will have any completed assessments included in the data summary.

KeraNetics, LLC. CONFIDENTIAL Page 24

Version: 00

Effective Date:

03-01-2018

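### Section 12.1 tests skin appearance with Fisher's exact test and does not say how 4 to 6 repeat ratings become one value per subject; a subject-level summary and a less conservative exact test would gain power at almost no cost

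*Combined protocol and SAP*

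**What the plan says.** Section 12.1 (Description of Statistical Methods) gives the whole analysis of this outcome in one sentence: a Fisher's "exact test will be used to compare skin appearance issues between the groups". It names no visit, no coding of an issue as present or absent, no summary over visits, no significance level and no sidedness.

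The data come from repeated assessments. At each weekly visit during radiotherapy, Section 6.5.2 records the physician's "assessment of skin dryness, appearance of inflammation" and the natural barrier. Section 6.5.3 repeats this at close-out. The synopsis gives 5 to 7 visits in total. Section 11.2 makes skin appearance a study endpoint, and the synopsis (Statistical Methods, Effectiveness) lists it with the DLQI and RTOG scores among the outcomes to be tested.

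On numbers, Section 12.2 says "Participants will be randomized equally (n=12 per group) to standard of care or KeraStat Cream" and also "Up to 26 subjects will be enrolled on this pilot study to assure completion of at least 24 subjects". Section 12.3 adds "All information for withdrawing subjects will be included in the analyses". The statement that comparisons "will have 80 percent power to detect a difference of 1.2 standard deviations" is made for RTOG and DLQI only; no power is claimed for skin appearance.

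**The concern.** Fisher's exact test on a two-by-two table takes one yes/no per independent unit, here the woman. With several ratings each, the sentence in Section 12.1 can be carried out in at least four ways: test one chosen visit, test ever/never, test every visit separately, or pool all ratings. The first leaves most of the data out of the test. The second reduces a course of ratings to one bit and loses duration. The third produces 4 × 3 = 12 to 6 × 3 = 18 tests over the three items, with none named as the one that counts. The fourth treats repeats on one woman as independent and is not valid. The text does not choose, so the choice could be made after the data are seen.

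Fisher's test is also markedly conservative at this sample size. The pilot exists to inform a larger trial, and a bare Fisher p-value supplies neither an effect estimate nor an interval for that purpose.

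**Working it through.** **Inputs.** 12 per arm, possibly 13 (Sections 12.2 and 12.3: 26/2 = 13, withdrawals kept). Post-baseline ratings: 5 − 1 = 4 to 7 − 1 = 6. Assumed, because the documents are silent: two-sided 5%, yes/no coding of each item, issue prevalences by arm, and within-subject correlation.

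**1. The plan's own figures.** For the t-test, the noncentrality is 1.2 × √(12/2) = 2.939 with 22 df and critical value 2.074, giving power 0.802 at two-sided 5%. The maximum margin for compliance is 1.96 × √(0.25/12) = 0.283. Both reproduce, which supports taking two-sided 5% as the intended level.

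**2. True size of Fisher's test.** With a and b subjects showing the issue out of n per arm, and R the set of rejected tables,

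size(p) = Σ over (a,b) in R of C(n,a) C(n,b) p^(a+b) (1−p)^(2n−a−b), maximised over p.

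- n = 12: Fisher rejects 60 of 169 tables; maximum size 2.28%, at p = 0.5.
- n = 13: Fisher rejects 76 of 196 tables; maximum size 2.90%.

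Boschloo's test uses Fisher's p-value as its statistic and raises the cut-off until the maximum size is as close to 5% as it can be without exceeding it. It rejects every table that Fisher rejects plus 12 more at either n. Maximum size is 4.5% at n = 12 and 4.9% at n = 13. One added table at n = 12 is 4/12 v 0/12, where Fisher's p = 2 × C(12,4)/C(24,4) = 2 × 495/10,626 = 0.093.

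**3. Power for one yes/no per subject, 12 per arm (enumerated).**

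| True rates | Fisher | Boschloo | Ratio |
|---|---|---|---|
| 30% v 0% | 0.276 | 0.507 | 0.54 |
| 48% v 31% | 0.072 | 0.118 | 0.61 |
| 50% v 10% | 0.425 | 0.588 | 0.72 |
| 70% v 30% | 0.389 | 0.454 | 0.86 |
| 80% v 20% | 0.812 | 0.848 | 0.96 |

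These rates are illustrations. The 48% and 31% are moist-desquamation rates cited in Section 4.2, not rates for these items.

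**4. Using all ratings.** Simulation, 20,000 trials per setting, 12 per arm, 4 to 6 yes/no ratings, the same prevalence at every visit, latent correlation 0.3 to 0.9. The all-visit comparator is a t-test on each subject's mean over visits, with null rejection about 5%. For 70% v 30% and 5 ratings:

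| Correlation | Fisher, one visit | Fisher, ever/never | All-visit mean | Ratios |
|---|---|---|---|---|
| 0.3 | 0.386 | 0.182 | 0.911 | 0.42, 0.20 |
| 0.5 | 0.388 | 0.276 | 0.823 | 0.47, 0.34 |
| 0.7 | 0.390 | 0.330 | 0.730 | 0.53, 0.45 |
| 0.9 | 0.389 | 0.363 | 0.619 | 0.63, 0.59 |

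Over all settings with a true difference, the ratio runs from 0.092/0.717 = 0.13 (ever/never, 6 ratings, 60% v 30%, correlation 0.3) to 0.811/0.947 = 0.86 (one visit, 5 ratings, 80% v 20%, correlation 0.9). Constant prevalence favours averaging, so a second model let it change over time: control prevalence 15/35/55/70/60%, a 1.2 SD shift in latent severity, correlation 0.3 to 0.7. Power was 54–61% for Fisher on ever/never, 45–51% for Fisher on one late visit, and 78–93% for a rank test on each subject's share of ratings with the issue. With prevalence 5/10/20/30/25% and correlation 0.5, the figures were 45%, 12–18% and 62–63%.

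**5. Two cautions on the remedy.** Pooling all ratings into one Fisher table gave type I error of 7–16%, so it must be ruled out. A plain share is distorted when subjects contribute different visits. With the first set of prevalences, a full course averages (15+35+55+70+60)/5 = 47%, but a woman who leaves after two ratings averages (15+35)/2 = 25%, which looks like benefit. With 4 of 12 in one arm leaving after two ratings and no true effect, rejection rose to about 8%.

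**The case against.** Fisher's test is valid and standard for small two-by-two tables, and conservatism is not an error. The primary objectives are feasibility and data for a later trial, the synopsis describes the results as descriptive, and skin appearance is not in its listed evaluation criteria. No power is promised for it. Preferring Boschloo's test or a rank test could be called a matter of taste. All of this stands as a limit on severity. It does not remove the gap: the synopsis and Section 12.1 both commit to a test, and the variable being tested is undefined.

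A reader might infer more than the documents support:

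- *That the plan discards the weekly ratings.* It is silent. Ever/never or worst rating would draw on every visit, and visit-by-visit tests would use them all.
- *That it will pool ratings.* Nothing in the text says so; the inflated error in step 5 is a reason to exclude pooling, not a fault found.
- *That a fixed fraction of power, such as half to two thirds, is lost.* The fraction depends on prevalences, correlation and how visits are collapsed, none of which is given. The 1.2 SD effect is stated for RTOG and DLQI only.
- *That ever/never must hit a ceiling because about 85% of patients react.* That figure in Section 4.1 is for moderate-to-severe skin reactions in radiotherapy patients, not for these three items.
- *That 2.3% is the ceiling for this trial.* It is 2.9% at 13 per arm, and would differ again if graded ratings were tested in a larger table.

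**Conclusion.** The concern holds as a cheap improvement; the plan is not wrong as written. Two parts are firm, given yes/no coding and two-sided 5%. Fisher's true size is at most 2.3% at 12 per arm (2.9% at 13), and Boschloo's test rejects everything Fisher does and more while staying under 5%. The resulting gain is 17 points at 50% v 10% (59% v 42%) but only 4 points at 80% v 20% (85% v 81%). A third part is firm from the text alone: Section 12.1 does not say how repeat ratings become one value per subject.

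The direction of the further gain from a per-subject summary is consistent across every setting with a true difference that was tried. Its size is not established: Fisher's share of the all-visit power ranged from about 0.13 to 0.86 under assumed rates and correlations. The remedy also needs protection against unequal follow-up.

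**What to change.** In Section 12.1, replace the Fisher sentence with text to this effect:

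> For each item (dryness, inflammation, natural barrier), a subject's score is the share of her ratings, over a common set of scheduled post-baseline visits, at which the issue was present. Arms are compared by an exact (permutation) Wilcoxon rank-sum test at two-sided 5%, and the difference in mean share is reported with its 95% CI. A sensitivity analysis addresses subjects who withdraw early or have shorter courses, by comparison visit by visit or by a permutation test stratified by visit. Where a single yes/no per subject is compared, Boschloo's exact test is used. Ratings are not pooled across visits as independent observations.

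Two definitions must go with it: when a rating counts as issue present, and which visits form the common set. A course with 5 visits in total has 5 − 2 = 3 on-treatment ratings plus follow-up, so a set shared by all subjects would have four ratings. Later on-treatment ratings could be shown descriptively.

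The cost is one paragraph, with no new data and no change in sample size. The downsides are that the share weights all visits equally, that a common set leaves the extra visits of longer courses out of the main comparison, and that the withdrawal sensitivity analysis is required.

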12.2. Sample Size

Up to 26 subjects will be enrolled on this pilot study to assure completion of at least 24 subjects. The expected accrual rate is four per month with accrual lasting approximately six months. Participants will be randomized equally (n=12 per group) to standard of care or KeraStat Cream. With 12 participants in each treatment group expected to complete the study, we will be able to calculate a 95% confidence interval around the compliance rate in each group with a maximum margin of error of 0.283. Comparisons between groups for effectiveness (RTOG scale and DLQI score) will have 80 percent power to detect a difference of 1.2 standard deviations.

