1. SYNOPSIS

Name of Company:Name of Product:Type of Study:KeraNetics, LLCKeraStat® CreamClinical Proof of Concept

Title of Study: Pilot Study: KeraStat® Cream for Radiation Dermatitis

Investigator(s): [name], PhD; [name], PhD

Study Period: Estimated screening expected to start March 2018; Expected completion September 2018

Phase of Development: Design & Development (Phase 3 of Design Control)

Objective(s):

Primary:

- To assess feasibility (compliance of use)
- Collect data for designing a larger future trial evaluating KeraStat Cream

Secondary:

- To assess the safety and tolerability of KeraStat Cream in subjects at risk of radiation dermatitis
- To assess the effectiveness of KeraStat Cream compared to standard of care to manage the symptoms of radiation dermatitis in subjects being treated with radiation therapy
- To estimate amount of KeraStat Cream used per patient and coverage on skin

Methodology: This is a randomized, open label study.

Number of Subjects:

Sufficient subjects will be screened and enrolled such that 24 total subjects, 12 subjects per treatment group, will complete the study through the Follow-Up Visit. With 12 participants in each treatment group, we will be able to calculate a 95% confidence interval around the compliance rate in each group with a maximum margin of error of 0.283. Comparisons between groups for effectiveness will have 80 percent power to detect a difference of 1.2 standard deviations. Results of the current study are intended to provide descriptive endpoint data to inform the design of a future clinical evaluation of product effectiveness.

Study Overview:

Study Periods:

The length of study participation for a subject is about 8-12 weeks, depending on the length of radiation treatment. The study will extend 4-6 weeks beyond the end of radiation therapy. The study will begin with a Screening Visit during treatment planning followed by weekly assessments during radiation therapy, and a follow up visit 4-6 weeks after completion of therapy. There is a total of 5-7 visits.

Study Assessments:

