6. INVESTIGATIONAL PLAN

6.1. Overall Study Design

This is a single site, between subject, open-label comparison pilot study to assess the feasibility and effectiveness of KeraStat Cream in managing RT skin toxicity. The length of study participation for a subject is 8-12 weeks depending on when a subject returns for her final follow-up evaluation. The Study Design Schematic is shown below in Figure 1 with the Acceptable Study Windows in Table 2.

Sufficient subjects will be screened such that 24 total subjects will complete the study. Patient compliance is expected to be good, so a target recruitment of 26 subjects is desired.

Once a RT patient is determined to be a candidate for inclusion in this study, they may be approached for consent to participate. A total of 26 breast cancer patients scheduled to receive RT will be recruited and consented.

RT will begin 4 to 10 weeks after surgery; the targeted volume will be the ipsilateral breast with or without regional lymph nodes. Once the patient has consented to participate in the study, their baseline pre-RT assessments can be completed during the radiation treatment-planning process.

Patients are generally treated with RT Monday through Friday, with weekends and holidays off, for approximately 4 to 6 weeks. Patients will be provided with KeraStat Skin Cream for application as often as needed but at least twice daily, morning and evening.

During the course of treatment, the patient sees the radiation oncologist weekly in clinic to review the patient's treatment course, monitor the skin's appearance after application of KeraStat Skin Cream or standard of care, and answer questions. Breaks in the treatment schedule should be avoided whenever possible, but breaks necessitated by RT skin toxicity or for other reasons will be recorded. The radiation oncologist will see each patient in follow-up 4-8 weeks after completing RT to assess the patient for RT-induced skin and other toxicities that may have occurred.

Version: 00

Effective Date: 03-01-2018

Figure 1: Study Design Schematic

Table 2: Acceptable Study Windows

Visit	Day Visit	Acceptable Visit Window
Screening (Visit 1)	Day 1	None
Baseline (Visit 1)	Day 1	None
First evaluation (Visit 2)	RT Day 8	±2 days
Second evaluation (Visit 3)	RT Day 15	±2 days
Third evaluation (Visit 4)	RT Day 22	±2 days
Fourth evaluation (Visit 5)	RT Day 29	±2 days
Fifth evaluation (Visit 6)	RT Day 36	±2 days
Final evaluation (Visit 7)	Post RT Day 30	±14 days

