6.3. Number of Subjects

Twenty-six subjects are anticipated to be required for screening and enrollment in order to achieve a total of 24 patients participating in this study. Subjects will be randomized to receive either standard of care or KeraStat Cream.

Subjects at screening will be given a sequential subject number starting with 1001, 1002, etc. Subject initials will be collected, but not used as an identifier. The subject number will be used to identify the subject and all study materials associated with each subject.

Version: 00

Effective Date:

03-01-2018

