7.3.2. Patient Withdrawal (Premature Discontinuation from the Study)

A documented effort must be made to determine why a subject fails to return for the necessary visit or is dropped from the study, and the reason for withdrawal must be recorded in the source documents and case report form (CRF). A subject may withdraw or be removed from the study for any of the following reasons and will be treated as considered appropriate by the Investigator:

- Subject request (for any reason)
- In the opinion of the Investigator, continuation is not in the best interest of the subject
- A serious or unexpected AE occurs such that continuation in the study is inappropriate
- Pregnancy
- RT is stopped
- In the opinion of the Sponsor, continuation is not in the best interest of the subject

If a subject is prematurely discontinued from participation in the study for any reason, the Investigator must follow up on all ongoing adverse events (if any).

In the event a subject is prematurely discontinued from the study due to an AE, or unexpected AE or serious adverse event (SAE) (as defined in Section 11.5.1), the procedures stated in Sections 11.3-11.9 must be followed.

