7.3.3. Replacement of Patients

Subjects will not be replaced.

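### Does the sample-size section need changing because 26 enrolled subjects, without replacement, cannot guarantee 24 completers, and because the end date and a visit label disagree with other sections?

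*Combined protocol and SAP*

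**What the plan says.** Section 12.2 (Sample Size) reads "Up to 26 subjects will be enrolled on this pilot study to assure completion of at least 24 subjects". It then bases its precision and power on a softer premise: "With 12 participants in each treatment group expected to complete the study". At 12 per group it claims a maximum margin of error of 0.283 for the compliance rate, and 80% power for a difference of 1.2 SD.

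Other sections bear on the count:

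- Section 7.3.3: "Subjects will not be replaced".
- Section 7.3.2: "A subject may withdraw or be removed from the study for any of the following reasons", followed by six reasons.
- Section 6.1: "Patient compliance is expected to be good, so a target recruitment of 26 subjects is desired", and also "A total of 26 breast cancer patients scheduled to receive RT will be recruited and consented".
- Section 6.3: "Twenty-six subjects are anticipated to be required for screening and enrollment".
- Synopsis: enough subjects will be enrolled that "24 total subjects, 12 subjects per treatment group, will complete the study through the Follow-Up Visit", with no upper limit given.

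On timing, the Synopsis expects screening from March 2018 and completion in September 2018, with 8-12 weeks of participation per subject. Section 12.2 expects four subjects a month for about six months.

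On completion, Section 7.3.1 requires the entire study through the final evaluation, which it numbers Visit 5 or 6. Table 2 in Section 6.1 numbers the final evaluation Visit 7 and gives Visits 5 and 6 to RT Days 29 and 36. The Synopsis gives a total of 5-7 visits.

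**The concern.** A ceiling of 26, no replacement and a firm promise of 24 completers do not fit together unless losses are known to be very low, and the plan states no loss rate. The only support is a general expectation of good compliance. Sections 6.1 and 6.3 also count the 26 at consent or screening, so a screen failure could use up part of the two-subject allowance. If completers fell short, the stated margin and power might not be met.

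The calendar and the visit label add to the impression that the section was not checked against the rest of the protocol. Six months of accrual followed by two to three months per subject should run past September. Read literally, Visit 5 or 6 could count a subject as complete during radiotherapy. A primary objective of the pilot is to inform a larger trial, so a wrong completer count or timeline could carry over into that design.

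**Working it through.** **The plan's own figures.** Inputs from Section 12.2: n = 12 per group, 95% interval, 1.2 SD. The protocol gives no alpha or sidedness; I assume two-sided 5%.

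- Largest margin (Wald, p = 0.5): 1.96 × √(0.25/12) = 0.283. This agrees.
- Power of the two-sample t-test (noncentral t) at 1.2 SD, 12 per arm: 0.802. This agrees. The difference detectable with 80% power is 1.20 SD.

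**The inflation from 24 to 26.** The allowance is 2/26 = 7.7%, and 24/(1 − 2/26) = 26. The number is arithmetically sound for that loss.

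**How sure 24 completers are.** With independent losses at an assumed rate d,

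P(at least 24 of 26) = (1−d)^26 + 26·d·(1−d)^25 + 325·d²·(1−d)^24.

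At d = 0.05 this is 0.264 + 0.361 + 0.237 = 0.861. The last column assumes 13 per arm and squares the chance of at least 12 of 13; it matches the 12-per-group target more closely.

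| Assumed loss | P(at least 24 of 26) | P(at least 12 of 13 in both arms) |
|---|---|---|
| 2% | 0.985 | 0.947 |
| 3% | 0.958 | 0.890 |
| 5% | 0.861 | 0.747 |
| 7.7% | 0.677 | 0.542 |
| 10% | 0.511 | 0.386 |

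A 95% chance of 24 completers needs a loss of about 3.2% or less. At 7.7%, 24 is only the expected number.

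**What a shortfall would cost.** Precision depends on subjects analysed, not on completers:

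| Analysed per arm | Margin | Power at 1.2 SD | Detectable at 80% power |
|---|---|---|---|
| 13 | 0.272 | 84% | 1.15 SD |
| 12 | 0.283 | 80% | 1.20 SD |
| 11 | 0.295 | 76% | 1.26 SD |
| 10 | 0.310 | 72% | 1.32 SD |

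Section 12.3 keeps all information from withdrawn subjects. Compliance is an average number of applications per week, and RTOG grade is recorded weekly, so a subject who leaves early can still contribute to both. Fewer than 24 completers therefore does not by itself mean 11 or 10 analysed per arm. If all 26 contribute, the 13-per-arm row applies.

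**The calendar.** Start on 1 March 2018, four per month, evenly spaced.

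- Earliest: the 24th subject enters after 23/4 = 5.75 months, about 23 August. The shortest Table 2 path is 28 days of RT plus 16 days (post-RT Day 30 minus 14), 44 days in all. That ends about 6 October.
- With 8 weeks of participation instead, the same subject ends about 18 October.
- Slowest: 26 subjects over 6.5 months, about 14 September, plus 12 weeks ends about 7 December.

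The overrun past 30 September is thus about 6 days to about 10 weeks. A start later in March adds up to a month. Working back from 30 September, entry would have to stop by 5 August (8 weeks) or 8 July (12 weeks). That allows about 5.16 × 4 = 20.6 or 4.24 × 4 = 17.0 subjects.

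**The visit label.** Counting Visit 1, the weekly RT evaluations and the final visit in order, a 4-week course ends at the fifth visit (Days 8, 15, 22), a 5-week course at the sixth (adding Day 29) and a 6-week course at the seventh (adding Day 36). Section 7.3.1 appears to use this ordinal count and leaves out the seventh. Table 2 uses fixed labels.

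**The case for a change.** The best argument for acting is that the edits are nearly free and the contradictions are real: a guarantee without a rate behind it, a cap in Section 12.2 that the Synopsis lacks, three bases for counting 26, an end date that the stated accrual does not reach, and a visit number that fails for 6-week courses. A pilot whose output is planning information should state its own planning assumptions correctly. Section 12.1 also calls its feasibility measure a completion rate, which might seem to let the loose definition in 7.3.1 into a primary measure.

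Most of the facts stand, but the consequence does not. Section 12.2 itself goes on to speak of 12 per group as expected, and Sections 6.1 and 6.3 call 26 a target and an anticipated number. A reader would take it as a planning figure with a two-subject allowance. Softening one verb would not raise the chance of 24 completers. The list of withdrawal reasons says nothing about how often they occur. The dates are given as estimated and expected and the accrual as approximate, so the mismatch is an optimistic administrative forecast. The completion-rate link is weak, because the same sentence in 12.1 goes on to classify participants by applications per week, as do the Synopsis and Section 11.1. The requirement in 7.3.1 to finish the entire study already rules out stopping at RT Day 29 or 36.

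**Conclusion.** No change to the plan is needed. The inconsistencies are genuine but clerical, or are missing detail that the study team can supply in conduct and reporting. The margin of 0.283 and the 80% power at 1.2 SD are right at 12 analysed per arm. Twenty-six follows from 24 at a 7.7% loss. Losing one analysed subject per arm from 12 would move the margin only to 0.295 and the power to 76%, and Section 12.3 makes even that less likely. No test, analysis set, decision rule or conclusion depends on the word used for the completion target, on the September date or on the visit number.

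This rests on a two-sided 5% t-test, which the protocol does not state but which reproduces its power figure, and on assumed, independent losses for every completion probability. It also rests on the study's descriptive purpose: a confirmatory trial that depended on a fixed number of completers would need a stated loss rate. If the protocol is amended for another reason, the wording of the target, the basis for counting 26, the end date and the visit label could be reconciled in the same pass.
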